5.16.1. Treatment-Emergent Adverse Events

Treatment-emergent AEs are defined as the reported AEs that first occurred or worsened during the postbaseline phase compared with baseline phase. For events occurring on the day of first administration of study drug, the case report form collected flag will be used to determine whether the event was pre-treatment versus post-treatment. For each TEAE, the severity level of the event (mild, moderate, or severe) will be determined by patient or physician opinion. The Medical Dictionary for Regulatory Activities (MedDRA) Lowest Level Term (LLT) will be used in the treatment-emergent computation. For each LLT, the maximum severity at baseline will be used as the baseline severity. If the maximum severity during postbaseline is greater than the maximum baseline severity, the event is considered to be treatment emergent. For events with a missing severity during the baseline period, it will be treated as “mild” in severity; for events with a missing severity during the postbaseline period, it will be treated as “severe” for TEAE computation. For each patient and TEAE, the maximum severity for the MedDRA level being displayed (PT, High Level Term, or SOC) is the maximum postbaseline severity observed from all associated LLTs mapping to that MedDRA level.

For events that are male- or female-specific, the denominator and computation of the percentage will only include patients from that specific sex.

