5.1. Overall Design

Study CGAR is a Phase 3b single-arm, open-label safety study of galcanezumab 300 mg in outpatients with episodic or chronic cluster headache who completed Study CGAL or Study CGAM.

Please refer to the Protocol Operations Manual for information regarding the schedule of activities, study design, study tools, and patient scenario examples.

The study will consist of 2 SP:

- SP I is the screening phase to confirm patients meet the inclusion/exclusion criteria.
- SP II is the open-label treatment phase during which patients can receive galcanezumab 300 mg administered subcutaneously (SC) up to once a month.

Study Phase I: SP I is the screening phase. Patients will sign an informed consent document prior to completing any study-related screening procedures. SP I is the time from Visit (V)1 to V2. The minimum timeframe for SP1 needs to allow sufficient time for patients to washout of any excluded medications and to review subject eligibility. Visit 1 will be considered complete when the last procedure of the screening assessment for the patient is completed. Once Study CGAR is open for enrollment, potentially eligible patients may enter screening directly from the parent study, CGAL or CGAM. If a patient is not experiencing cluster headache attacks (e.g., in remission) they may wait to enter screening for CGAR until they anticipate experiencing or are experiencing a cluster headache attack. If patients had completed the parent study, CGAL or CGAM, prior to Study CGAR being open for enrollment, potentially eligible patients may still enter screening for Study CGAR. Study procedures for V1 (Event List A) of Study CGAR will be completed as follows:

- If the last visit of the parent study is also the first visit of Study CGAR, then electrocardiograms (ECGs), vitals, weight, hematology, clinical chemistry, urinalysis, hemoglobin A1C (HbA_{1C}), and serum pregnancy, C-SSRS, and Self-Harm Supplement Form/ Self-Harm Follow-up Form (SHSF/SHFU) from the last visit of the parent study will also be used for the first visit of Study CGAR.
- If the last visit of the parent study is ≤ 2 weeks from V1 of Study CGAR, the hematology, chemistry, HbA_{1C}, and urinalysis do not need to be repeated.
- If the last visit of the parent study is > 2 weeks from V1 of Study CGAR, all study procedures in Event List A need to be completed at the first visit of Study CGAR.

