Note: After V1, if V2 does not occur within 3 months of V1 (e.g., patient enters V1 in remission), prior to V2 an ECG, hematology, clinical chemistry, urinalysis, urine drug screen (UDS), HbA_{1C}, and serum pregnancy must be collected and eligibility confirmed prior to dosing at V2 (see footnote “d” in the SOA).

Study Phase II: SP II is the single-arm open-label treatment phase during which patients can receive galcanezumab 300 mg administered SC up to once a month. If a patient meets all eligibility requirements, a urine pregnancy screen will be conducted at the first dosing visit, prior to dosing to confirm that a female patient is not pregnant before administering investigational product. Following the first dose of galcanezumab, the patient should remain in the office for 30 minutes of observation. The site will have a scheduled telephone visit (V3) with the patient approximately 1 week after the first investigational product administration to collect spontaneously reported AEs.

Every month, the decision whether to administer a monthly dose will be based upon the study investigator’s judgment, which is not limited to, but includes assessment of the patient’s clinical symptoms and response as follows:

- Dosing is up to once monthly; more frequent dosing is not allowed. The full 300 mg dose is to be administered, changing the dose amount is not allowed.
- If the patient remits and dosing is halted, the patient may remain in the study, but they should have an office visit 1 month after the last dose to complete the procedures listed in

Event List F (Table 2.1). Dosing in this scenario may be reinitiated at the study investigator's discretion.

- Monthly telephone visits should be completed for patients who are not being dosed, but remain in the study (e.g., in remission).
- If dosing is temporarily interrupted due to a potential safety concern, dosing may be reinitiated at the study investigator's discretion following a discussion and agreement between the study investigator and Lilly Medical that re-initiation of dosing is appropriate.
 - At the office visit **prior to re-initiation of dosing** the following procedures: ECG, immunogenicity, pharmacokinetics (PK), hematology, clinical chemistry, HbA1c and urine pregnancy are to be collected. The urine pregnancy must be negative and the ECG should be evaluated for safety prior to dosing.

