9.2.1. Serious Adverse Events

An SAE is any AE from this study that results in 1 of the following outcomes:

- death
- initial or prolonged inpatient hospitalization
- a life-threatening experience (that is, immediate risk of dying)
- persistent or significant disability/incapacity
- congenital anomaly/birth defect
- considered significant by the investigator for any other reason: important medical events that may not result in death, be life-threatening, or require hospitalization may be considered serious, based upon appropriate medical judgment.
- when a condition related to the disposable manual prefilled syringe necessitates medical or surgical intervention to preclude either permanent impairment of a body function or permanent damage to a body structure, the serious outcome of “required intervention” will be assigned.

Although all AEs occurring after signing the ICF are recorded in the eCRF, SAE reporting begins after the patient has signed the ICF and has received investigational product. However, if an SAE occurs after signing the ICF, but prior to receiving investigational product, it needs to be reported ONLY if it is considered reasonably possibly related to study procedure.

Study site personnel must alert Lilly or its designee of any SAE within 24 hours of investigator awareness of the event via a sponsor-approved method. If alerts are issued via telephone, they are to be immediately followed with official notification on study-specific SAE forms. This 24-hour notification requirement refers to the initial SAE information and all follow-up SAE information.

Pregnancy (during maternal or paternal exposure to investigational product) does not meet the definition of an AE. However, to fulfill regulatory requirements any pregnancy should be reported following the SAE process to collect data on the outcome for both mother and fetus. Pregnancy cases should be reported up to 5 months after last investigational product administration.

Investigators are not obligated to actively seek AEs or SAEs in subjects once they have discontinued and/or completed the study (the patient summary eCRF has been completed). However, if the investigator learns of any SAE, including a death, at any time after a subject has been discharged from the study, and he/she considers the event reasonably possibly related to the study treatment or study participation, the investigator must promptly notify Lilly.

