5.4. General Considerations

General aspects of statistical analyses are described below.

Unless otherwise specified, analyses will be conducted in the GMB-treated population, which includes all patients who are enrolled and receive at least 1 dose of study drug in Study CGAR, and analyses will be presented with 1 treatment arm. Safety analyses will be performed during the GMB-treated time and during the whole open-label treatment phase (SP II), which includes both GMB-treated time plus off-treatment time. GMB-treated time is composed of monthly dosing intervals, that is, the time from a GMB dose to the next monthly visit. The time between the first monthly visit that a dose is not administered and the dosing re-initiation visit is counted as off-treatment time. Baseline will be the time during SP I prior to receiving the first dose in this study. For safety analyses during the open-label treatment phase, any time after the first dose of GMB 300 mg will be considered as postbaseline period no matter if it is during an on-treatment or off-treatment month. For safety analyses during the GMB-treated time, only events that occurred during the GMB-treated time will be considered as postbaseline values.

Statistical analysis of this study will be the responsibility of Lilly or its designee. SAS[®] software will be used to perform most or all statistical analyses.

Any change to the data analysis methods described in the protocol will require an amendment ONLY if it changes a principal feature of the protocol. Any other change to the data analysis methods described in the protocol, and the justification for making the change, will be described in the SAP or clinical study report (CSR). Additional exploratory analyses of the data will be conducted as deemed appropriate.

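### Baseline severity for TEAEs is the maximum over a screening phase with no stated upper limit, so an event that ended before the first dose can mask later episodes of the same term

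*SAP*

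**What the plan says.** The rule has three parts.

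- **Baseline period.** SAP 5.4: "Baseline will be the time during SP I prior to receiving the first dose in this study". Protocol 5.1: "SP I is the time from Visit (V)1 to V2". Only a lower bound on its length is described: "The minimum timeframe for SP1 needs to allow sufficient time for patients to washout of any excluded medications". A longer interval is foreseen: "After V1, if V2 does not occur within 3 months of V1 (e.g., patient enters V1 in remission"). In that case tests are repeated and eligibility is confirmed again, but nothing restarts the adverse event baseline.
- **Events that enter it.** Protocol 9.2.1: "all AEs occurring after signing the ICF are recorded in the eCRF". Neither TEAE section limits baseline events to those still ongoing at the first dose.
- **Comparison.** SAP 5.16.1: "For each LLT, the maximum severity at baseline will be used as the baseline severity". It then states: "If the maximum severity during postbaseline is greater than the maximum baseline severity, the event is considered to be treatment emergent". Protocol 10.3.4 has the same rule, so the two documents agree.

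A missing severity is set to mild at baseline and to severe after baseline. Both settings lean towards counting the event.

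**The concern.** A maximum over the whole of SP I treats a resolved event as if it were still the patient's state at the first dose. It then sets the threshold for that LLT for the rest of follow-up, which Protocol 3.1 says may last months or years. SP I length differs between patients, so the proportion with a given TEAE depends partly on how long patients waited in screening. In a single-arm study no comparison group shares that effect.

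TEAEs are one of the three primary endpoint components in Protocol Table 4.1. A masked episode that is serious or leads to discontinuation should still appear, because SAP 5.16 lists separate tables for those events. A masked episode that is neither has no other frequency table among the CGAR-alone analyses. The hypersensitivity and injection-site summaries count TEAEs, and the registry category for non-serious events (SAP 5.18) requires TEAE status. Acute recurrent terms are the most exposed, and upper respiratory tract infection is a named event of interest (SAP 4.2).

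**Working it through.** The plan states no TEAE rate, SP I duration or sample size calculation, so there is no figure to reproduce. I made three checks.

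**1. The rule as written, per LLT**

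| Maximum in SP I | Later maximum mild | Later maximum moderate | Later maximum severe |
|---|---|---|---|
| none | TEAE | TEAE | TEAE |
| mild | masked | TEAE | TEAE |
| moderate | masked | masked | TEAE |
| severe | masked | masked | masked |

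Masking holds however many later episodes occur and however long ago the SP I event ended. A recurrence coded to a different LLT still counts.

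**2. Size for one LLT**

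Every input here is an assumption:
- rate r = 0.1, 0.3 or 0.6 per patient-year, the same before and after the first dose;
- gamma-distributed between patients with coefficient of variation (CV) 1;
- severity 60% mild, 35% moderate, 5% severe;
- SP II length T = 1 year, SP I length S = 1 or 3 months;
- all SP I events captured.

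With CV 1, the probability of no event over exposure x is L(x) = 1/(1 + r·x). Let G(k) be the share of events more severe than level k: G(0) = 1, G(1) = 0.40, G(2) = 0.05, G(3) = 0.

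- True proportion with an episode after the first dose: 1 − L(T).
- Counted as TEAE: the sum over k of P(SP I maximum = k and later maximum > k). For k = 0 the term is L(S) − L(S + T). For k = 1 and 2 it is [L(S·G(k)) − L(S·G(k−1))] − [L((S + T)·G(k)) − L(S·G(k−1) + T·G(k))]. For k = 3 it is zero.

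Example, r = 0.6 and S = 0.25 years:
- true: 1 − 1/1.6 = 37.50%
- k = 0: 0.8696 − 0.5714 = 0.2981
- k = 1: (0.9434 − 0.8696) − (0.7692 − 0.7194) = 0.0240
- k = 2: (0.9926 − 0.9434) − (0.9639 − 0.9174) = 0.0027
- counted: 32.49%; relative loss (37.50 − 32.49)/37.50 = 13.4%

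| Rate | True % | Counted, SP I 1 month (loss) | Counted, SP I 3 months (loss) |
|---|---|---|---|
| 0.1 | 9.09 | 8.99 (1.1%) | 8.79 (3.3%) |
| 0.3 | 23.08 | 22.40 (2.9%) | 21.16 (8.3%) |
| 0.6 | 37.50 | 35.68 (4.8%) | 32.49 (13.4%) |

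If only half of SP I events are captured (r halved in SP I only), the 3-month losses fall to 1.7%, 4.3% and 7.1%. A wider grid (rates 0.1 to 1.0, CV 0 or 1.5, severity split 50/40/10 or 70/25/5, SP II of 1 or 2 years) gives about 2-20% at 3 months.

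**3. Effect on the percentage with any TEAE**

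Take ten independent LLTs at 0.1 per year each, no between-patient variation, severity 50/40/10 and 1 year of SP II. The true figure of 63.2% is counted as 62.5% after a 3-month SP I, a drop of 0.7 points. Even after a 12-month SP I it is 60.5%, a drop of 2.7 points. Any distortion is therefore mainly in term-level rows.

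**The case against.** The strongest reply has four parts.

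- **Discounting what the patient already had is the purpose of treatment emergence.** The protocol glossary defines a TEAE as absent before treatment or worse than the pretreatment state, and Protocol 10.3.4 fixes the rule. Replacing it would count relapsing pre-existing complaints and would weaken comparability with the sister studies and the integrated analyses. This stands as a reason to leave the main definition alone. It does not argue against a supportive table.
- **Much of the waiting may fall outside SP I.** Protocol 5.1 lets a patient in remission delay entering screening, and that time precedes V1. This stands. The same section also gives entry at V1 in remission as an example of a long SP I, so both routes are open.
- **Capture in SP I is thin.** Table 2.1 schedules adverse event collection at V1 and Month 0 with nothing between, and the repeat tests after 3 months include no adverse event item. Minor resolved events may be missed and so cannot mask anything. This stands, and it is why the figures above are towards the high side for the rates assumed.
- **Upper respiratory infections are grouped by two High Level Terms (SAP 5.16.4), while masking acts per LLT.** A later infection coded to another LLT still counts. This reduces the effect without removing it.

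A reader might infer that the primary endpoint as a whole is undercounted. The documents do not support that. SAEs have their own table and are counted in the registry output regardless of TEAE status, and SAP 5.16.5 counts any positive C-SSRS answer during treatment. A reader might also extend the model to a 6- or 12-month SP I, where losses at rates of 0.3 to 0.6 reach about 15-24% and 27-39%. No document gives SP I lengths of that order, or says that episodic patients would make up most of the long waits.

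**Conclusion.** The mechanism is real and follows from the text. It can undercount the TEAE component for recurrent terms in patients with a long SP I. The loss is limited to later episodes of the same LLT at equal or lower severity, and it is invisible elsewhere only when those episodes are non-serious and do not lead to discontinuation.

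Whether an undercount occurs, and how large it is, cannot be known from the documents. The illustrative loss of 1-5% at 1 month and 3-13% at 3 months rests on the assumed rates, severity mix, CV of 1, 12 months of SP II and full capture in SP I. It is smaller if capture is incomplete, and patients who roll over quickly are barely affected. This is an analysis choice that merits a supportive analysis. It is neither a conflict between protocol and SAP nor a reason to discard the main rule.

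**What to change.** Keep the protocol rule as the main TEAE definition. Add to SAP 5.16.1 one supportive table, by PT within SOC and for upper respiratory tract infections. In that table, baseline severity comes only from events ongoing at the first dose. Any adverse event that starts after the first dose then counts as treatment-emergent if the earlier SP I episode of that LLT had ended. Events on the day of the first dose can use the case report form flag that 5.16.1 already specifies. Report the distribution of SP I duration (first to last, with median and quartiles) beside the table, so that readers can judge how much masking was possible.

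The cost is SAP wording, one programmed table from adverse event start and end dates, and one duration summary. Protocol 10.3.1 and SAP 5.4 require a protocol amendment only for a change to a principal feature, and a supportive table does not alter the main definition. The downside is that some relapsing pre-existing complaints will count in the supportive table, so its percentages will be somewhat higher and should be labelled accordingly.

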5.16.2. Potential Hypersensitivity Events

Potential hypersensitivity events will be defined using the following terms (standard MedDRA query [SMQ]):

- broad and narrow terms in the “Anaphylactic reaction” SMQ (20000021)
- broad and narrow terms in the “Angioedema” SMQ (20000024)
- broad and narrow terms in the “Hypersensitivity” SMQ (20000214)

A listing of patients having an event identified from these analyses will be medically reviewed to determine if the terms identified represent events likely hypersensitivity in nature. Listings should include information on timing of event relative to latest dose of study drug administration, the event term from this query, other AEs for the patient and timing, any abnormal laboratory findings, concomitant medication, medical history and pre-existing

conditions. Only those that are judged medically to be events likely hypersensitivity in nature will be included in the final summary.

The number and percentage of patients with likely hypersensitivity TEAEs will be summarized by treatment groups using MedDRA PT nested within the SMQ. Events will be ordered by decreasing frequency within the SMQ.

5.16.3. Adverse Events Related to Injection Sites

Adverse events related to injection sites will be defined using terms from the MedDRA High Level Term “Injection site reactions.”

The number and percentage of patients with TEAEs related to injection sites will be summarized using MedDRA PT. Events will be ordered by decreasing frequency of PT term.

5.16.4. Upper Respiratory Tract Infections

Upper respiratory tract infections will be defined using all the PTs from the 2 High Level Terms of “upper respiratory tract infections” and “upper respiratory tract infections NEC” as defined in MedDRA.

5.16.5. Suicide-Related Thoughts and Behaviors

Postbaseline suicidal ideation, suicidal behavior, and self-injurious behavior without suicidal intent, based on the C-SSRS, will be summarized for the GMB-treated population during GMB-treated time and GMB-treated time plus post-treatment time. In particular, for each of the following events, the number and percent of patients with the event will be enumerated: completed suicide, nonfatal suicide attempt, interrupted attempt, aborted attempt, preparatory acts or behavior, active suicidal ideation with specific plan and intent, active suicidal ideation with some intent to act without specific plan, active suicidal ideation with any methods (no plan) without intent to act, nonspecific active suicidal thoughts, wish to be dead, and self-injurious behavior without suicidal intent.

In addition, the number and percent of patients who experienced at least one of various composite measures will be presented and compared. These include suicidal behavior (completed suicide, non-fatal suicidal attempts, interrupted attempts, aborted attempts, and preparatory acts or behavior), suicidal ideation (active suicidal ideation with specific plan and intent, active suicidal ideation with some intent to act without specific plan, active suicidal ideation with any methods [no plan] without intent to act, non-specific active suicidal thoughts, and wish to be dead), and suicidal ideation or behavior.

Specifically, the following outcomes are C-SSRS categories and have binary responses (yes/no). The categories have been re-ordered from the actual scale to facilitate the definitions of the composite and comparative endpoints, and to enable clarity in the presentation of the results.

Category 1 – Wish to be Dead

Category 2 – Non-specific Active Suicidal Thoughts

Category 3 – Active Suicidal Ideation with Any Methods (Not Plan) without Intent to Act

Category 4 – Active Suicidal Ideation with Some Intent to Act, without Specific Plan

Category 5 – Active Suicidal Ideation with Specific Plan and Intent

Category 6 – Preparatory Acts or Behavior

Category 7 – Aborted Attempt

Category 8 – Interrupted Attempt

Category 9 – Actual Attempt (non-fatal)

Category 10 – Completed Suicide

Self-injurious behavior without suicidal intent is also a C-SSRS outcome (although not suicide-related) and has a binary response (yes/no).

Composite endpoints based on the above categories are defined below.

- Suicidal ideation: A “yes” answer at any time during treatment to any 1 of the 5 suicidal ideation questions (Categories 1-5) on the C-SSRS.
- Suicidal behavior: A “yes” answer at any time during treatment to any 1 of the 5 suicidal behavior questions (Categories 6-10) on the C-SSRS.
- Suicidal ideation or behavior: A “yes” answer at any time during treatment to any 1 of the 10 suicidal ideation and behavior questions (Categories 1-10) on the C-SSRS.

Patients who discontinued from the study with no postbaseline C-SSRS value will be considered unevaluable for analyses of suicide-related events. Only evaluable patients will be considered in the analyses.

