9.2.1.1. Suspected Unexpected Serious Adverse Reactions

Suspected unexpected serious adverse reactions (SUSARs) are serious events that are not listed in the IB and that the investigator identifies as related to investigational product or procedure. United States 21 CFR 312.32 and European Commission Clinical Trial Directive 2001/20/EC (United States Government Publishing Office [WWW]; European Commission [WWW]) and the associated detailed guidances or national regulatory requirements in participating countries require the reporting of SUSARs. Lilly has procedures that will be followed for the recording and expedited reporting of SUSARs that are consistent with global regulations and the associated detailed guidances.

9.2.1.2. Adverse Event Monitoring with the Columbia-Suicide Severity Rating Scale, Self-Harm Supplement Form, and Self-Harm Follow-up Form

The C-SSRS and SHSF will be administered to assess and evaluate patients for suicide-related events (behavior and/or ideation) at every scheduled and unscheduled office visit as specified in the Schedule of Activities (Table 2.1). Before administering the C-SSRS (Posner et al. 2011), study site personnel will question the patient about any change in the pre-existing condition(s) and the occurrence and nature of any AEs. Nonserious AEs obtained through the questionnaire are recorded and analyzed separately. Only *serious* AEs and AEs leading to discontinuation elicited through the C-SSRS are to be recorded as AEs via eCRF. Serious adverse events must be reported to Lilly or its designee within 24 hours as SAEs. The SHSF captures the number of discrete events of suicidal behavior, possible suicidal behavior, or nonsuicidal self-injurious behavior recorded in the C-SSRS and must be completed at every visit. Additionally, the SHFU will be completed at any visit, including screening/baseline visits, when a suicidal or nonsuicidal self-injurious behavior is identified. At any time during the study, if a patient is considered to be at significant risk for suicide by the investigator, prompt referral of the patient to a mental health professional should be considered.

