Suicidal ideation, suicidal behavior, and non-suicidal self-injurious behavior based on the C-SSRS will be summarized. For each of the following events, the number and percentage of patients with the event will be enumerated: completed suicide, non-fatal suicide attempt, interrupted attempt, aborted attempt, preparatory acts or behavior, active suicidal ideation with specific plan and intent, active suicidal ideation with some intent to act without specific plan, active suicidal ideation with any methods (not planned) without intent to act, nonspecific active suicidal thoughts, wish to be dead, and non-suicidal self-injurious behavior. In addition, the number and percentage of patients who experienced at least 1 of the composite measures during SP II will be presented. These include suicidal acts (completed suicide and nonfatal suicidal attempts), suicidal behavior (suicidal acts, interrupted attempts, aborted attempts, and preparatory acts or behavior), treatment-emergent suicidal ideation or treatment-emergent suicidal behavior.

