- Safety analyses are reduced to summaries of AE overview, TEAE, SAE, and DCAE, since detailed planned analyses of Study CGAR safety data are more thoroughly described in PSAP for cluster headache indication in the context of combining the safety data from the originating studies with the safety data from Study CGAR.
- Section 5.17. Reports to Be Generated at Each Interim and Final Database Lock was added.
- Other minor corrections, modifications, and clarifications were made.

Statistical Analysis Plan Version 3 was approved prior to the final study database lock. The overall changes and rationale for the changes incorporated in Version 3 are as follows:

- General formatting and grammatical edits were made to improve clarity.
- The PGI-I analyses in Section 5.13 were updated to remove a graphical display; a tabular summary will be presented instead, without 95% confidence intervals.
- The description of the EQ-5D-5L questionnaire was updated in Section 5.14 to provide additional details for the derivation of the health state index scores. A description of the correlation analyses of EQ-5D-5L with PGI-I and cluster headache status was also added to meet the stated tertiary objectives.
- The following safety analysis descriptions were added in Section 5.16, to be consistent with the analysis approaches described in the SAPs for the other Emgality Phase 3 cluster headache studies:
 - Potential hypersensitivity events (Section 5.16.2)
 - AEs related to injection sites (Section 5.16.3)
 - Upper Respiratory Tract Infections (Section 5.16.4)
 - Suicide-related thoughts and behaviors (Section 5.16.5)
 - Vital signs and weight (Section 5.16.6)

- Electrocardiogram Intervals and Heart Rate (Section 5.16.7)
- Laboratory tests (Section 5.16.8)
- Immunogenicity (Section 5.16.9)
- The data cutoff dates for the two interim database locks were added in Section 5.17.1 for the interim locks used to support the regulatory submission and safety update report, respectively.
- The list of important protocol deviations in Appendix 1 were updated to align with the current version of the Trial Issue Management Plan (Version 12).

4. Study Objectives

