A shift table summary of qualitative ECGs at any time will be produced, to assess shifts from baseline normal to postbaseline abnormal for the overall ECG and for each of the 11 finding categories mentioned above.

Patients with the following are excluded from ECG analyses: lead reversals or <9 leads, nonmatching demographic data, and those suggesting patient identification errors.

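### SAP 5.16.5 drops the protocol's treatment-emergent C-SSRS composite, so the CGAR tables for a primary endpoint cannot separate new or worsened ideation from ideation already present before the first CGAR dose

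*SAP*

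**What the plan says.** Protocol Table 4.1 lists the C-SSRS with TEAEs and SAEs as the primary endpoints. Protocol 10.3.4 plans three composites over SP II: suicidal acts, suicidal behavior, and "treatment-emergent suicidal ideation or treatment-emergent suicidal behavior". The protocol defines treatment-emergent for adverse events but not for the C-SSRS.

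SAP 5.16.5 also has three composites, but a different set: ideation, behavior, and either. Ideation is a yes "answer at any time during treatment to any 1 of the 5 suicidal ideation questions (Categories 1-5) on the C-SSRS". The other two follow the same pattern for Categories 6-10 and 1-10. The section limits the data to postbaseline records and treats patients who discontinue with no postbaseline C-SSRS as unevaluable. It never refers to the patient's baseline answers. It adds that "the number and percent of patients who experienced at least one of various composite measures will be presented and compared", without naming a comparison.

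The SAP's revision history says that Version 3 added 5.16.5 and seven other safety sections "to be consistent with the analysis approaches described in the SAPs for the other Emgality Phase 3 cluster headache studies". It also records that Version 2 had cut back the CGAR-only safety analyses because a program-level plan (the PSAP) covers them more fully. Neither entry mentions a dropped composite. SAP 5.4 says that a change to the protocol's methods, and "the justification for making the change, will be described in the SAP or clinical study report (CSR").

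**The concern.** CGAR has one arm, so the patient's own pre-dose status is the only reference inside the study. A percentage of patients with any ideation during treatment mixes two groups: those whose ideation appeared or worsened after the first CGAR dose, and those who already had it and stayed the same. The protocol's composite was meant to isolate the first group, and the SAP's composites do not.

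Baseline ideation is possible under the entry rules. Exclusion 12 removes patients whom the investigator considers at significant suicide risk, not everyone with a baseline yes. Exclusion 11 lets in patients with stable major depressive disorder.

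The SAP uses baseline elsewhere: for adverse events, vital signs, ECG, laboratory tests and antibodies. For ECG it says "A shift table summary of qualitative ECGs at any time will be produced, to assess shifts from baseline normal to postbaseline abnormal". That creates no duty for the C-SSRS, but it shows that the approach is already in the SAP's toolkit, while a primary endpoint goes without it.

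**Working it through.** **Step 1. Compare the composites.**

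| Composite | Protocol 10.3.4 | SAP 5.16.5 |
|---|---|---|
| Suicidal acts | Planned | Absent; both components tabulated singly |
| Suicidal behavior | Planned, no baseline reference | Kept, no baseline reference |
| Treatment-emergent ideation or treatment-emergent behavior | Planned | Absent |
| Any ideation | Not listed | Added (Categories 1-5) |
| Any ideation or behavior | Not listed | Added (Categories 1-10) |

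The protocol's stand-alone behavior composite was never treatment-emergent, so nothing changed there. Losing suicidal acts costs little, because its parts are still shown. The material loss is the treatment-emergent composite, mainly its ideation part.

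**Step 2. Does postbaseline supply the missing reference?** No. It sets the time window. A patient with the same ideation category before and after the first dose still counts.

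**Step 3. Do the AE tables fill the gap?** In part. Under Protocol 9.2.1.2, only serious events and "AEs leading to discontinuation elicited through the C-SSRS are to be recorded as AEs via eCRF". Ideation mentioned when staff ask about adverse events before giving the scale can also be recorded. For the rest, "Nonserious AEs obtained through the questionnaire are recorded and analyzed separately". Ideation that is nonserious, does not lead to discontinuation and is elicited only by the scale therefore depends on 5.16.5.

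**Step 4. Direction and bound.** Take treatment-emergent to mean new or worse than before the first CGAR dose. Let N be the evaluable patients, k those with any postbaseline yes, and b those among the k who also had ideation or behavior at baseline.

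- SAP count = treatment-emergent patients + patients whose postbaseline yes is no worse than baseline.
- The second group lies within b, so the treatment-emergent count is between k - b and k.
- Maximum overstatement = b/N.

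**Step 5. Illustration.** The documents give no N, k or b, so all three are assumptions. One baseline case (b = 1) adds at most:

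- N = 100: 1/100 = 1.0 percentage point
- N = 150: 1/150 = 0.67
- N = 200: 1/200 = 0.5
- N = 250: 1/250 = 0.4

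With k = 8 and N = 200, the SAP reports 8/200 = 4.0%. The treatment-emergent figure would be:

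| b | Lower limit | Range |
|---|---|---|
| 0 | 8/200 | 4.0% |
| 1 | 7/200 | 3.5% to 4.0% |
| 2 | 6/200 | 3.0% to 4.0% |
| 4 | 4/200 | 2.0% to 4.0% |

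The planned C-SSRS tables do not show b, so a reader could not tell which row applies.

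**Step 6. Are the data there?** Yes. Table 2.1 schedules the C-SSRS at Visit 1 and Month 0, and footnote j puts injections after all other visit procedures.

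**The case against.** The other side has a good deal of substance.

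- **The SAP count is conservative.** This stands. A reader might infer that the SAP hides new cases. It does not: among evaluable patients, any new or worsened ideation recorded on a postbaseline C-SSRS is in the count. What is lost is the ability to tell it from the rest.
- **No rule is broken.** This stands. A reader might infer a breach of SAP 5.4, but that section lets the change and its reason appear in the CSR instead, and the CSR is not before us. The revision history gives general reasons for the section and for the earlier reduction. It simply does not identify this change.
- **CGAR baseline is not a drug-free baseline.** This stands and matters. SAP 5.16.9.2 puts prior galcanezumab at 0 to 15 months: none for CGAL placebo patients, 2 months for CGAL active, 12 or 15 for CGAM. Under Table 2.1, footnote a, the Visit 1 C-SSRS can be the parent study's last one. A reader might infer that baseline ideation is unrelated to drug and that the treatment-emergent count is the true one. The documents support neither. Ideation that began on galcanezumab in a parent study would count as baseline and drop out of a treatment-emergent count, while the SAP's count keeps it if it persists. Both counts are needed.
- **The effect may be nil.** Possible. Exclusions 11 and 12 may keep b small, and at b = 0 the two definitions agree.
- **The integrated analyses may cover it.** SAP 5.16 refers to separate documents, which were not available. Protocol 10.3.4, however, plans the composite for this study, and SAP 5.16 lists suicide-related output for CGAR alone.

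**Conclusion.** The point holds as a mismatch between protocol and SAP on a primary endpoint. Two planned composites are missing. The loss of the treatment-emergent one means that the CGAR C-SSRS tables cannot separate new or worsened ideation from ideation present before the first CGAR dose. The count is over-inclusive by at most b/N. That size cannot be computed from the documents and may be zero.

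This rests on reading treatment-emergent as new or worse than before the first CGAR dose, since the protocol does not define the term for the C-SSRS. It concerns the CGAR outputs only. It does not show that cases are missed, that data are lacking or that SAP 5.4 was breached. The item is modest but worth correcting, because the output was planned and the data exist.

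**What to change.** In SAP 5.16.5:

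1. Keep the any-postbaseline table.
2. Restore the treatment-emergent composite with a stated definition and denominator. One option is ideation that is new or in a higher category than the worst before the first CGAR dose, or new postbaseline suicidal behavior. State that the Month 0 pre-dose C-SSRS counts as baseline. Protocol 10.3.1 implies this, but SAP 5.4 ties baseline to SP I, while Table 2.1 appears to place Month 0 in SP II.
3. Present it beside the any-postbaseline count, ideally with a table of worst baseline category by worst postbaseline category.
4. Add the caveat that baseline follows 0 to 15 months of prior galcanezumab. Show results by the three prior-exposure groups in SAP 5.16.9.2, or at least state the limitation.
5. If the composite is not restored, record the change and its reason in the SAP or the CSR.

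Two smaller points. Deleting *compared*, or naming the comparison, is editorial. It would also help to say whether a completed suicide recorded before any postbaseline C-SSRS makes the patient evaluable; the death would appear among the SAEs in any case.

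The cost is SAP wording, one or two tables and minor programming on data already collected. No new assessments and no protocol change are needed.
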